I (investigator) agree to ensure that no research activity or recruitment will commence at participating research sites until the appropriate regulatory approvals and NHS confirmations of Capacity and Capability have been issued, and Sponsor green light confirmed.

I (investigator) also confirm that I will make the findings of the study publicly available through publication or other dissemination tools without any unnecessary delay and that an honest, accurate and transparent account of the study will be given. Any deviations from the study as planned in this protocol will be explained and reported accordingly.

Chief Investigator:

Signature: Date: 05/JUN/2025

Print Name (in full): [name].....

Position:Professor of Gastroenterology and Biophotonics.....

On behalf of the Study Sponsor:

Signature: Date...../.....

Print Name (in full):

Position:

STUDY SUMMARY

IDENTIFIERS	
IRAS Number	353916
REC Reference No.	
Sponsor Reference No.	179418 University College London Joint Research Office, UCLH/UCL Joint Research Office, part of the Research Directorate, [name]
Other research reference number(s) (if applicable)	Z6364106/2025/02/142
Full (Scientific) title	Assessing relative effectiveness of Artificial Intelligence air Safety Tool (AISaT) recommendations in outpatient, day-case rooms, and wards to reduce risks of airborne disease transmission
Health condition(s) or problem(s) studied	Airborne disease transmission in hospitals
Study Type i.e. Cohort etc	A series of Randomised Controlled Trials
Aim(s):	To assess relative effectiveness of recommendations made by the Air Safety artificial intelligence Tool (AISaT) to reduce risks of airborne disease transmission
Objectives:	
These trials are to investigate:
 
 A) whether placing mitigations for airborne disease transmission according to the recommendations of the AISaT software tool reduces airborne disease transmission risks in outpatient consulting rooms, aerosol generating procedure rooms and hospital wards. B) Whether it is feasible to implement these mitigations at different hospital sites (and identify any variation in implementation). C) whether patients and hospital staff find the AISaT recommendations acceptable 
Primary Objective: To determine in hospital consulting rooms, aerosol generating procedure rooms and wards, when using mitigations for airborne disease transmission according to recommendations of the AISaT software tool, the reduction in the relative number of airborne aerosol droplets per standard time period breathed by any staff member present compared to when no mitigations are used or when mitigations are used as decided by the clinician using the relevant space.

	
Outcome Measure: Number of aerosol droplets on average per minute per clinical encounter as measured by an air particle counter (APC) installed next to the clinician and at up to 4 other fixed locations in the room or ward bay.
 
Secondary Objective: Mixed methods evaluation of staff experiences of using the tool and the mitigation approaches that are recommended (based on analysis of acceptability by staff and feasibility of implementation).
 
Outcome Measures:
 
 1. Normalisation Measure Development Questionnaire (NoMAD) 2. Ethnographic observations using formal and informal interviews to explore hospital staffs' views on the importance of AISaT, usability and management of the AISaT software and challenges to fidelity in implementation, and how team members can work together effectively to support implementation 3. An estimation of the cost efficiency of AISaT
Type of trial:	A two-site 3*3 cross-over randomised controlled trial
Trial design and methods:	
The trial will be run as a staged series of randomised control trials (RCTs), each one in a different clinical location. They will each be preceded by a pilot phase. The locations are in increasingly complex areas. The first location will be an outpatient consulting room. The second will be in a room where aerosol generating procedures (AGP) are performed, e.g. in endoscopy or in ENT, and the third will be an inpatient ward bay with approximately 6 beds.
 
Before the RCTs commence, a pilot phase will identify the optimal settings to use (see trial design section).
 
Each RCT stage will then be run in a cross-over format with aerosol droplet generation determined by outcomes of the pilot phase. The first two RCT stages will involve hospital clinicians running a weekly session in the same clinic or AGP room. There will be different configurations each week, which will be allocated randomly, to allow direct comparison. Configuration 1: The AISaT will be turned on and air quality safety measures will be implemented. These may include the use of air filters, fans, screens etc. Configuration 2: AISaT will be turned off completely with no extra air quality safety measures and Configuration 3: Air quality safety measures will be offered to the clinician to use and place as they see fit. The order of these 3 different configurations will be randomised.
 
54 clinicians (and their patients) will be invited to join, equating to roughly 27 clinicians per hospital. All patients attending either their outpatient clinic appointment or their AGP will be invited to join.
 
A small aerosol-producing device(s) will be installed within the room to generate saline aerosol droplets and air particle counters (APCs) will be installed next to participating clinicians to measure the primary outcome, which is the average number of aerosol droplets per minute

	
per clinical encounter as measured by an air particle counter (APC) installed next to the clinician and at up to 4 other fixed locations in the room or ward bay.
 
In Stage 3 of the RCT, the same three configurations described above will be arranged in 12 ward bays (6 in each hospital), each for one day, in random order. Here, the clinician making the decision for configuration 3 will be the senior nurse for the ward.
 
Running alongside all stages of the trial will be a mixed methods evaluation. This will include usability testing and exploratory research interviews with a subset of clinicians, patients and other relevant hospital staff such as nurses, estates staff and infection prevention and control (IPC) staff in the pilot phase, and a process evaluation during the main RCT stages.

Trial duration per participant:	
Clinicians: 3 weeks
 
Patients in outpatient clinic/ having an AGP: 1 day
 
Ward patients and clinicians: 3 days
 
For those patients or staff involved in the mixed methods evaluation, trial duration will last no more than 4 months.

Key Study milestones:	
Each trial is due to complete within 6 months, with 3 months as a buffer to deal with any unforeseen issues.
 
Month 3: Completion of first pilot phase
 
Month 9: Completion of first clinical trial in outpatient consulting rooms
 
Month 12: Completion of second pilot phase
 
Month 18: Completion of 2nd clinical trial in AGP rooms
 
Month 21: Completion of third pilot phase
 
Month 27: Completion of 3rd clinical trial in ward bays/ Data envelope analysis completed
 
Qualitative and quantitative data collection for the process evaluation will run alongside the clinical trials and will also be complete by month 27.

Estimated total trial duration:	
Anticipated start date: 1st July 2025
 
Anticipated end date: 30th September 2027

Planned trial sites:	
Multi-site:
 
 1. UCL Hospitals NHS Foundation Trust 2. Lister Hospital (East and North Hertfordshire NHS Trust)
Total number of participants planned:	
Stage 1 Pilot: Outpatient clinic rooms
 
12 sessions
 
Up to 12 clinicians

10 patients + 5 accompanying persons each per clinic = 120 patients + 60 accompanying persons = 180 + 12 clinicians

Total = 192

Stage 1: Outpatient clinic rooms

27 clinicians x 2 hospitals = 54 clinicians

10 patients + 5 accompanying persons per clinic = 540 patients + 270 accompanying persons x 3 weeks = 2430:

Total = **2484**

Stage 2 Pilot: AGP Procedure Rooms

9 sessions

Up to 9 clinicians

10 patients per session per clinician = 90 patients

Total = **99**

Stage 2: AGP Procedure Rooms

27 clinicians x 2 hospitals = 54 clinicians

10 patients per session per clinician = 540 patients x 3 weeks = 1620

Total = **1674**

Stage 3 Pilot: Wards

3 days

Approximately 6 beds in 1 bay. As days may not be consecutive, aim for up to 18 patients

Day nurse & night nurse = 2 per day so **6** in 3 days

Day HCA and night HCA = 2 per day so **6** in 3 days

Up to 3 doctors per day = **9** in 3 days

Total = **18+6+6+9 = 39**

Stage 3: Wards

Each of the 2 hospitals has 6 bays, each bay containing 6 beds. This gives a total of 72 beds.

25% patient turnover rate (72×1.25) = approximately **90** patients in 3 days.

Day nurse & night nurse = 12 per 24 hour period, so **36** in 3 days

Day HCA and night HCA = 12 per 24 hour period, so **36** in 3 days

6 doctors per day = **18** in 3 days

Total = **90+36+36+18= 180**

For each stage, we will also speak to **up to 30** other staff members including estates, infection prevention and control, managers and other relevant staff groups in each hospital. We will conduct

	
ethnographic observations, and informal interviews with infection control leads, clinical and estates staff to consider use of ventilation devices, how they are deployed, how are they used, challenges and solutions to their use - and we will perform up to 15 semi-structured interviews with management leads, clinical and estates staff. With observations.
 
Total = 30 x 2 hospitals x 3 stages = 180
 
Overall total = 192+2484+99+1674+39+180+180= 4848 participants

Inclusion criteria:	
Clinicians working at relevant clinical testing environments (1st trial outpatient clinic room, 2nd trial AGP room, 3rd trial ward bay)
 
All patients (and accompanying persons) attending in those relevant clinical testing environments
 
The mixed method evaluation may include people working in estates teams, hospital managers and other healthcare staff.

Exclusion criteria:	
Obstetric, psychiatric and paediatric clinical areas will be excluded, to minimise the risks of ethical complications involving children, pregnant women or patients with psychiatric illnesses that may have difficulty consenting.
 
People under the age of 18 years old will be excluded

Statistical methodology and analysis:	
Clinical trials: Data analysis will be linear mixed modelling controlling for confounding factors which may include number of people in the room, baseline ventilation, room size, room shape, temperature, humidity and various other factors (see full list of suggested confounding factors in study design section).
 
Process evaluation: Descriptive statistics will be used to present the findings from the NoMAD questionnaire.
 
Observations will be analysed using framework analysis, organised according to the core constructs of Normalisation Process Theory (NPT) using the format of context, mechanism, and action according to each observation.
 
Based on these data a convergence coding matrix will be generated using normalisation process theory (NPT).
 
Pilot phase:

---------------------------------------	--

	
Semi-structured interviews will use framework analysis, guided by the core constructs of the NPT.
 
Qualitative data analysis in the evaluation phase will be carried out using the RREAL Sheet for real-time analysis and framework analysis for in-depth analysis.
 
Health economics:
 
Data envelope analysis (DEA) to rank the efficiency of AlSaT in removing air droplets in different settings.
 
Cost-utility analysis to calculate the mean incremental cost of AlSaT compared to current practice. This will be calculated using information from the DEA combined with data from the literature on the relationship between air droplets and common air born infections such as influenza.

FUNDING & OTHER	
Funding	This work is funded by the National Institute for Health and Care Research (NIHR) under its Programme Grants for Applied Research Programme (Ref: NIHR205439).
Other support	N/A
STORAGE of SAMPLES / DATA (if applicable)	
Human tissue samples	N/A

	
This 'local' privacy notice sets out the information that applies to this particular study. Further information on how UCL uses participant information can be found in our 'general' privacy notice:
 
For participants in health and care research studies, please visit this weblink for further information:
 
https://www.ucl.ac.uk/legal-services/privacy/ucl-general-privacy-notice-participants-and-researchers-health-and-care-research-studies
 
The information that is required to be provided to participants under data protection legislation (GDPR and DPA 2018) is provided across both the 'local' and 'general' privacy notices.

--	---

KEY ROLES AND RESPONSIBILITIES

SPONSOR: The sponsor is responsible for ensuring before a study begins that arrangements are in place for the research team to access resources and support to deliver the research as proposed and allocate responsibilities for the management, monitoring and reporting of the research. The Sponsor also must be satisfied there is agreement on appropriate arrangements to record, report and review significant developments as the research proceeds, and approve any modifications to the design.

FUNDER: The funder is the entity that will provide the funds (financial support) for the conduction of the study. Funders are expected to provide assistance to any enquiry, audit or investigation related to the funded work.

CHIEF INVESTIGATOR (CI): The person who takes overall responsibility for the design, conduct and reporting of a study. If the study involves researchers at more than one site, the CI takes on the primary responsibility whether he/she is an investigator at any particular site.

The CI role is to complete and to ensure that all relevant regulatory approvals and confirmations of NHS Capacity and Capability are in place before the study begins. Ensure arrangements are in place for good study conduct, robust monitoring and reporting, including prompt reporting of incidents, this includes putting in place adequate training for study staff to conduct the study as per the protocol and relevant standards.

1. INTRODUCTION

This series of sequential clinical trials is part of the Air Safety programme grant, funded in July 2024 by National Institute for Health and Care Research (NIHR), led by [name]. The clinical trials are due to take place from year 2 of the 5-year programme.

The Air Safety programme research team has developed an **Artificial Intelligence air Safety Tool (AISaT)**. AISaT is computer software that guides users on how to best reduce airborne infection risks in hospitals, using cheap solutions like air filters, fans and screens etc. Our research programme is investigating whether AISaT works, is acceptable and cost-effective. We will also develop guidance on how to use AISaT across the NHS. These clinical trials in 2 hospitals (UCLH and Lister hospital) are a key part of our research programme, to assess the effectiveness of AISaT recommendations in outpatient, aerosol generating procedure rooms, and wards to demonstrate reduced infection risks.

Our AISaT tool could allow higher hospital patient throughput while reducing risks of spreading airborne transmitted diseases such as influenza, respiratory syncytial virus and COVID-19. To do this, we need to understand how a successful AISaT tool would be implemented and what the barriers to that implementation might be. Alongside the clinical trials, we will undertake a series of studies using validated instruments to explore issues such as usability and acceptability to key stakeholders.

2. BACKGROUND AND RATIONALE

When people breathe, speak or cough, they spray saliva into the air. The smallest droplets, (aerosols), can remain suspended in the air for hours and spread widely. Viruses in these droplets can infect others, particularly indoors. Indeed, early in the COVID-19 pandemic, there were some high profile cases of super-spreading events such as the Shincheonji Church of Jesus in South Korea and the Sri Petaling mass gathering in Malaysia, which at one point accounted for more than 60% and 35% of cases in their respective countries, and were the largest clusters of infection within each country^{1, 2}. Adequate ventilation can effectively prevent accumulation.³ Increasing room air flow lowers risk but usually needs expensive building work and/or high energy costs. Simple, low-cost techniques to reduce infection risks are urgently needed. Many UK hospitals were built at a time when the importance of preventing airborne disease transmission was not adequately recognised. They may rely on passive ventilation through use of windows or have no ventilation whatsoever. Even newer hospitals with air conditioning may have been built to maximise energy efficiency with an inevitable trade off against air safety as recycling air increases the risks of transmitting airborne diseases. It is impractical to retrofit entire hospitals.

Inadequate hospital room airflow drove nosocomial disease transmission during the COVID-19 pandemic. Safeguarding against future respiratory viruses with a rapidly deployable technology is a critical NHS need. During the COVID-19 pandemic, multiple retrofit solutions were tried including screens, fans, high efficiency particulate air (HEPA) filters and ultraviolet C (UVC) air cleaning among others. But national advice on implementation was lacking, because nobody knew the best way to implement them. Research has dramatically increased, and we now know that they can reduce the

numbers of infective respiratory particles in the air, although the best way to deploy mitigation devices currently remains beyond our grasp.

What we are now very clear about is that the performance of mitigation devices is heavily driven by their location within the space they are employed.⁴ Airflow design and flow rates also have an important impact. Simulations of enclosed UVC air cleaning units suggest that positioning the device closest to the infectious source (if known) will provide the most benefit^{5,6}. Ventilation rates and air mixing in the room determine interactions between airborne virus and the mitigation strategy. Computational modelling studies have shown that repositioning a mitigation device on the opposite side of the room could reduce effectiveness by more than 50%.⁷ Several studies also show that room airflow mixing is important for UV systems located towards the roof of the room to perform effectively.⁸ This can be enhanced in some settings using mixing fans,⁹ although unexpected airflow patterns can result in diffusing a virus throughout a wider area.¹⁰

Studies on indoor aerosol transmission and air filtration in clinical settings pointed to a series of strategies to reduce the spread of COVID-19 in hospitals. The use of room air purifier units with HEPA filtration (free-standing or ceiling mounted) was one of the most widely recommended strategies¹¹. In terms of the use of devices for air cleaning, recent studies showed that inexpensive portable air cleaning devices, particularly those with HEPA filters, should be considered for small and enclosed spaces in healthcare settings, such as inpatient rooms and personal protective equipment donning/doffing stations.¹²⁻¹⁴ These portable air cleaning devices were identified as particularly important where there was limited ability to reduce aerosol transmission with building HVAC ventilation.¹⁵ Although it has not been definitively proven that reducing infective respiratory particle density leads to lower rates of infection, small studies do point toward an approximately 20% reduction in risk of disease spread when mitigations are put in place in environments akin to hospital wards such as care homes.¹⁶ This benefit does not appear to extend to kindergartens, where close contact between children and staff is likely to be ubiquitous.¹⁷ In situations of close contact, face masks are far more likely to reduce disease transmission.

One promising avenue towards filling the gaps in our knowledge on how to maximise the benefits of using mitigation devices is the use of computational modelling that offers the capability of predicting air flow efficiency in a variety of scenarios. AI technologies have been recently developed by our group and others to expedite analysis^{18,19}. Our work is now showing that this modelling can provide optimal mitigation strategies which are tailored to each individual clinical environment, and with further development it will be possible to generate this information almost real-time.²⁰ We have published a series of papers which demonstrate that we already have a basic AI driven tool for identifying the best ways to deploy the relevant solutions²¹⁻²³.

Air quality affects all, but there are particularly vulnerable populations, and these groups are over-represented in hospitals. People with underlying respiratory conditions are notably at increased risk as are those with immunosuppression from blood dyscrasias or undergoing chemotherapy for cancer.^{24,25} The elderly are all at higher risk due to the physiological senescence of the immune system, particularly in those with multiple comorbidities.²⁶ A very important group which came to

the fore during the recent pandemic is medical and other hospital staff. They were particularly badly affected during the early stages of the pandemic with infection rates not only many times higher than the general population, but also with prolonged side effects ('long Covid').^{27,28} This was particularly severe amongst frontline staff from ethnic minorities.²⁹ This is not new. Tuberculosis and norovirus have been noted to spread to frontline staff for many years.³⁰

It is worth emphasising one group again: hospital in-patients. During the COVID-19 pandemic, nosocomial transmission became a major source of morbidity and mortality. Safe air in hospitals is therefore likely to bring benefits to the most vulnerable patients and staff alike.

3. OBJECTIVES AND OUTCOME MEASURES/ENDPOINTS

3.1 Primary Objective

Primary Objective: To determine in hospital outpatient consulting rooms, aerosol generating procedure rooms and wards, when using mitigations for airborne disease transmission according to recommendations of the AISaT software tool, the reduction in the relative number of airborne aerosol droplets per standard time period which will be breathed by clinicians compared to when no mitigations are used or when mitigations are used as decided by the clinician using the relevant space.

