10.3 Sample size calculation

Participants: 3 consulting rooms or 3 AGP rooms in each hub hospital. 54 clinicians who regularly use these rooms (27 per hospital approximately) will be invited to take part, each for 3 consecutive weeks.

A 3-period, 3-treatment cross-over design will be used to test whether there is a difference in the 3 means. The comparison will be made using a Geisser-Greenhouse corrected F-test with a Type I error rate (α) of 0.05. The group means under the null hypothesis are assumed to be equal. The standard deviation across subjects at the same period is assumed to be 1 (and the means are expressed, see below, as a fraction of the standard deviation, which allows us to calculate a sample size using the Cohen's D approach). The assumed pattern of the covariance matrix is 'all correlations equal' (compound symmetry) with a correlation of 0.5 between adjacent time point measurements. To detect group means of '0 0.25 0.5' with 90% power, the needed number of clinicians is 53 (each measured 3 times). Given that there are six possible sequence combinations of the 3 treatments, the sample size is increased to the closest multiplicator of 6, which is 54. The sample size was computed using PASS 2024, version 24.0.2.

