10.8 Primary outcome analysis

Data analysis will be linear mixed modelling of the paired data (3 conditions for each clinician) controlling for confounding factors which may include: number of people in the room, baseline ventilation, room size, room shape, temperature, humidity and various other factors (see full list of suggested confounding factors in study design section). The power of the trial based on the UK sites alone is 90%.

Data analysis relies on properly functioning aerosol generators and particle counters. In stages 1 and 2, we will check each piece of machinery is working properly before the beginning of the clinical session. Where we do not manage to collect data for at least 2 hours in a clinical session, that session will be withdrawn from the study and repeated in its entirety. We expect this to happen in less than 5% of clinic sessions. For stage 3, a minimum of 6 hours data per day is required otherwise that day's randomisation will need to be rerun.

There are no plans for predefined subgroup analyses in stages 1 and 2. For stage 3, subgroup analyses will include daytime (8 am to 8pm) versus nighttime (8 pm to 8 am).

We will employ the intention-to-treat (ITT) analysis method to ensure the integrity and validity of our RCTs.

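### The primary objective asks for two AISaT comparisons, but the protocol fixes one omnibus test that answers neither and does not say which contrast supports which claim

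*Protocol*

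**What the plan says.** Three parts of the Protocol bear on what a stage is meant to show.

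- **Objective.** Section 3.1, and the Study Summary in near-identical words, asks for the reduction in droplets under AISaT "compared to when no mitigations are used or when mitigations are used as decided by the clinician using the relevant space". Objective A in the Study Summary asks "whether placing mitigations for airborne disease transmission according to the recommendations of the AISaT software tool reduces airborne disease transmission risks".
- **Sized hypothesis.** Section 10.3 uses the three-period cross-over "to test whether there is a difference in the 3 means". It adds: "The comparison will be made using a Geisser-Greenhouse corrected F-test with a Type I error rate (α) of 0.05". The means 0, 0.25 and 0.5 are not assigned to configurations.
- **Primary analysis.** Section 10.8 states: "Data analysis will be linear mixed modelling of the paired data (3 conditions for each clinician) controlling for confounding factors". It then gives the power of the trial as 90%. It names no contrast between configurations and does not carry the F-test forward.

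Stage 3 has 12 ward bays and, according to section 10.4, no formal sample size calculation.

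**The concern.** The two comparisons in the objective support different claims. AISaT versus no mitigation shows that devices put in a room where the software says remove droplets; any sensible placement might do the same. AISaT versus clinician placement is the comparison that tests the software's advice. The trial title is about the effectiveness of the recommendations. Section 2 stresses that device performance depends heavily on location, and section 6.1 describes the tool as choosing devices and their placement.

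An omnibus test of three means has no direction and does not show which configuration differs. It can be significant because of clinician placement alone. The objective, the sized hypothesis and the primary analysis therefore do not point to the same question. At stake is whether a positive stage is read as evidence for the recommendations when the data show only that devices beat no devices, or show nothing about AISaT at all.

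**Working it through.** **Inputs, all from section 10.3.** "The standard deviation across subjects at the same period is assumed to be 1"; compound symmetry "with a correlation of 0.5 between adjacent time point measurements"; alpha 0.05; "To detect group means of '0 0.25 0.5' with 90% power, the needed number of clinicians is 53 (each measured 3 times"; rounded up to 54 to fill six sequences.

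**The plan's own figure.** Under compound symmetry the within-clinician variance is 1 × (1 − 0.5) = 0.5. The squared deviations of 0, 0.25 and 0.5 from their mean sum to 0.125. The noncentrality is n × 0.125 / 0.5 = 0.25n, with 2 and 2(n − 1) degrees of freedom. Power is 89.9% at n = 52, 90.5% at 53 and 91.1% at 54. The stated 53 reproduces, as the sample size for the omnibus test.

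**Pairwise contrasts at n = 54.** The SD of a paired difference is √(2 × 0.5) = 1, so its standard error is 1/√54 = 0.136.

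- Difference 0.5 SD: noncentrality 0.5 × √54 = 3.67, power about 95%.
- Difference 0.25 SD: noncentrality 0.25 × √54 = 1.84, power about 44%.

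**What each decision rule does.** The table is from simulation at n = 54 (60,000 data sets per row, 200,000 for the first). Means are in SD units and lower is better. Contrasts are two-sided at 5%.

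| AISaT / none / clinician | F-test rejects | Either contrast favours AISaT | Same, only after significant F | Both contrasts favour AISaT |
|---|---|---|---|---|
| 0 / 0 / 0 | 5.0% | 4.5% | 2.1% | 0.5% |
| −0.5 / 0 / −0.5 | 97.1% | 95.4% | 94.4% | 2.4% |
| −0.25 / 0 / −0.25 | 45.2% | 44.8% | 36.3% | 2.2% |
| 0 / 0 / −0.5 | 97.1% | 2.6% | 2.6% | 0.0% |
| 0 / 0.5 / 0.25 | 91.1% | 95.8% | 90.9% | 43.9% |

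In row 2 AISaT equals clinician placement. The F-test rejects in 97%, and an either-contrast reading credits AISaT in about 95%, with or without the F-test as gate. In row 4 AISaT does nothing and only clinician placement works, yet the F-test again rejects in 97%. Row 5 uses the plan's means with AISaT best and clinician placement in the middle.

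**Family-wise error under the global null.** The two contrasts share the AISaT mean, so their correlation is 0.5. If both are tested ungated at two-sided 5%:

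- either direction: 1 − P(|Z1| < 1.96, |Z2| < 1.96) = 9.07%;
- in AISaT's favour only: 1 − P(Z1 < 1.96, Z2 < 1.96) = 4.5%.

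If the contrasts are tested only after a significant F-test, the rate in either direction is 4.2%.

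**The case against.** **'Or' is not a success rule.** Section 3.1 is an estimation objective that lists two reference conditions. Reporting both reductions with intervals would satisfy it, and a reader would then see a null AISaT-versus-clinician estimate. This stands. The Protocol nowhere says that either contrast is enough, so the 95% shows what such a reading would do, not what the plan prescribes.

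**A multiplicity rule may be in the SAP.** Contrast order and gatekeeping are commonly left to the SAP, which was not available here. This also stands, and the absence of such a rule is not the point made. The objective and the omnibus hypothesis are fixed in the Protocol itself, and they do not match.

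**A reader might infer that AISaT can be declared effective at about 9% family-wise error.** The documents do not support that. The figure needs two ungated, unadjusted two-sided 5% contrasts, which no section states, and it counts results against AISaT as well. In AISaT's favour the rate is about 4.5%. With three configurations, testing contrasts only after a significant F-test keeps the error within 5%.

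**Ordering the contrasts is not free.** Once a claim for the recommendations depends on AISaT versus clinician placement, the relevant power may be far below 90%. This is correct and belongs with the fix.

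**Conclusion.** The point holds as a mismatch between the primary objective and the hypothesis that the Protocol sizes, together with a primary analysis that does not link contrasts to claims. It does not hold as a demonstrated inflation of the 5% error rate. An F-test gate would deal with the error rate but not with the mismatch: in the equal-placement case, gated testing still credits AISaT in about 94% of trials under an either-contrast reading.

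The figures rest on the plan's SD of 1, correlation of 0.5 with compound symmetry, a normally distributed outcome, 54 clinicians and no dropout. The 44% also assumes that AISaT is best and clinician placement lies in the middle of 0, 0.25 and 0.5, which the plan does not say. The figures apply to stages 1 and 2 only, not to the 12 bays of stage 3.

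**What to change.** 1. In section 3.1 and the Study Summary, replace 'or' with an ordered pair of comparisons.
2. In section 10.8, name two mixed-model contrasts as primary for stages 1 and 2, in fixed sequence. Step 1 is AISaT versus no mitigation at two-sided 5%. Step 2, only if step 1 is significant in AISaT's favour, is AISaT versus clinician-placed mitigation at two-sided 5%.
3. State that step 1 alone supports only a claim for AISaT-placed devices against nothing, and that a claim for the recommendations over clinician judgement needs step 2 in AISaT's favour. Report clinician placement versus none descriptively.
4. Use the same order in stage 3, noting that it has no sample size calculation.
5. In section 10.8, describe the 90% as the power of the omnibus F-test. Give step 1 as about 95% for a 0.5 SD difference and both steps together as about 44% under the assignment above.

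The sequence needs no split of alpha. The change is to wording only, with no new data or participants. The costs are a narrower claim when only step 1 succeeds, no formal claim against clinician placement when step 1 fails, and open disclosure of the 44%. If the sponsor wanted 90% power for a 0.25 SD difference in AISaT versus clinician placement, about 170 clinicians would be needed (about 127 for 80%). That would be a separate decision.
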